4.7 Data Quality Assurance

4.7.1 Monitoring, Audits and Inspections

During the investigation, the monitor will have regular contacts with the investigation site. These contacts will include visits to confirm that the facilities remain adequate to specified standards and that the investigation site team is carrying out the procedure stated in the Clinical Investigation Plan and supports the investigator. All data must be accurately recorded in the CRF. Source data verification (a comparison of data in the CRF with the subject's hospital/practice and other records at the investigation site) with direct access to records will also be performed.

The monitor or other Mölnlycke Health Care personnel will be available between visits if the investigator or other staff at the site needs information and/or advice.

Authorized representatives of Mölnlycke Health Care and/or a Competent Authority (CA) and/or the Ethics Committee (EC)/Institutional Review Board (IRB) may visit the investigation site to perform audits/inspections, including source data verification.

Investigation Code	MxBFlex_02	Final Version	Approval date	2018-06-19
		Central Amendment 1	Approval date	2018-11-08
		Central Amendment 2	Approval date	

4.7.2 Training of Staff

The Principal Investigator will ensure that appropriate training relevant to the investigation is given to the medical, nursing and other staff at the site involved and that new information of relevance to the performance of this investigation is forwarded to the staff involved.

4.7.3 Data Management

The Data Management process includes all activities related to data handling regarding:

- Compilation of an eCRF
- Randomization
- Set-up of eCRF and database
- Specification of on-line checks
- Data entry / Data editing
- Export of data from Viedoc to SAS
- Creation of post-entry checks and listings
- Reconciliation of (SAE), (SADE), (ADE) and Device Deficiency (DD)
- Clean-file process including execution of post-entry checks and listings
- Post clean-file tasks

Viedoc, a web based electronic CRF system, will be used to capture data in this investigation. The eCRF system complies with FDA Title 21 CFR part 11 (ER/ES) requirement.

eCRF training will be given to appropriate personnel before/at initiation of the investigation site(s).

Data entry will be done by investigators and other authorized personnel at the site(s). When entering data on-line checks are incorporated in Viedoc for consistency and validation. Pharma Consulting Group will support with a helpdesk function taking care of system user questions regarding Viedoc.

When data has been entered authorized personnel at Mölnlycke Health Care can immediately view the data, send queries if necessary and lock eCRF pages when they have been validated.

Photos will be uploaded in Viedoc and are marked with the subject code. Uploaded photos shall not contain any information that can reveal the identity of the subject. All uploaded photos will be reviewed by personnel at Mölnlycke Health Care and stored in the company database. All data entered in Viedoc will be encrypted. The physical database will be stored in Sweden.

Programs for post-entry checks and data listings will be created and executed for validation of data.

Completeness will be checked by authorized personnel at Mölnlycke Health Care so that there are no unexplainable empty fields in Viedoc. This is done in order to prevent that data have been overlooked by personnel entering the data.

Investigation Code	MxBFlex_02	Final Version	Approval date	2018-06-19
		Central Amendment 1	Approval date	2018-11-08
		Central Amendment 2	Approval date	

A clean-file meeting will be held prior to database lock. All decisions on the evaluability of the data from each individual subject for the statistical analysis must be made and documented before locking the database.]

4.8 Statistical Methods and Determination of Sample Size

4.8.1 Statistical Evaluation

Two cross-over studies AB/BA will be performed. In the first one Mepilex® Border Flex will be compared with Optifoam and in the second one Mepilex® Border Flex will be compared with Allevyn Life. Exactly the same statistical methods will be used in both these cross-over studies. In this statistical section Optifoam and Allevyn Life will be substituted with active control.

Primary efficacy variable, days to strikethrough, and probably all of the other efficacy variables are non-normal distributed. Therefore, non-parametric tests are used.

it is likely the status of the wounds will be better in the second period of the cross-over. This implies that the statistical analysis must adjust for period effect in the AB/BA crossover study. For primary efficacy variable days to strikethrough, all other continuous outcome variables, all ordered categorical variables and all dichotomous variables the adjustment for period effect will be performed in the following way:

For all subjects the difference in the efficacy variable between Period 2 and Period 1 in the cross-over will be calculated.

These differences will then be compared between subjects started with Mepilex® Border Flex in Period 1 and subjects started with active control in Period 1 with an optimal two-sided two-sample test. For continuous variables the differences will be analyzed with Fisher's non-parametric permutation tests between the two groups and for ordered categorical variables and dichotomous variables the differences, number and percentages improved, not changed and worsened, will be analyzed with Mantel-Haenszel Exact Chi-square test.

The main statistical analysis will be performed on the full analysis set (ITT). Complementary statistical analysis will be performed on the Per Protocol (PP) set.

The Full Analysis Set will include all subjects with at least one measurement of follow up. The Per Protocol population will include all subjects that fulfil all inclusion/exclusion criteria and that are not described as protocol violators. They should have been followed for the 2x2 weeks treatment period. Subjects identified as protocol violators will be documented and agreed between Mölnlycke Health Care and the Principal Investigator before declaration of clean-file, please see Section 4.7.

The Safety population include all subjects that have at least one application of the Mepilex® Border dressing or at least one of the other study dressings.

Investigation Code	MxBFlex_02	Final Version	Approval date	2018-06-19
		Central Amendment 1	Approval date	2018-11-08
		Central Amendment 2	Approval date	

The distribution of continuous variables and change in continuous variables will be given as mean, standard deviation, median, minimum and maximum and the distribution of categorical and dichotomous variables will be given as numbers and percentages.

All statistical tests will be two-sided and conducted at the 5% significance level.

A baseline table will be given for all included subjects with the distribution of demographics and baseline variables.

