	
6. Is wound dressing completely saturated with strike through
 
Wound granulation
 
None
 
Trace islands of granulation tissue, less than 25%
 
25% - 49% Wound base is covered with granulation tissue
 
50% - 74% Wound base is covered with granulation tissue
 
75% - 99% Wound base is covered with granulation tissue
 
100% - Wound base completely filled with granulation tissue
 
(%, captured via photodigital planimetry and visual judgement by research doctor/nurse)
 
Non-viable tissue (eschar, fibrin slough, both)
 
None
 
Less than 25%
 
25% - 49%
 
50% - 74%
 
75% - 100%
 
(captured via photodigital planimetry and visual judgement by research doctor/nurse as above)
 
Wound size (captured via photodigital planimetry)
 
Rate of wound healing (%, captured via photodigital planimetry)
 
Condition of surrounding skin (Healthy/not healthy)
 
Signs of inflammation (erythema, edema, induration) (Y/N)
 
Signs of skin irritation at dressing site (Y/N)
 
Skin rash/skin erosion, eczema (Y/N)
 
Stasis dermatitis (Y/N)

--	---

Investigation Code **MxBFlex_02** **Final Version** **Approval date** **2018-06-19**
Central Amendment 1 Approval date **2018-11-08**
Central Amendment 2 Approval date

	
Vesicular erosion (blistering) (Y/N)
 
Skin maceration (None, Slight, Moderate, Severe)
 
Clinical signs/symptoms of acute infection
 
Increased pain and tenderness (Y/N)
 
Increased warmth (Y/N)
 
Sudden increase in ulcer size (Y/N)
 
Is there localized Erythema (Y/N)
 
Foul smelling exudates (Y/N)
 
Does the wound bleed easily (Y/N)
 
Wound odor (before and after cleansing)
 
(None, Minimal, barely noticeable, Moderate, noticeable but not offensive, Moderate, offensive, Putrid)

Safety Evaluation	Number of device related safety events associated with each of the wound dressings (ADEs/SADEs/DDs)
Patient-centric outcomes.	
Patient Reported outcomes
 
Pain
 
Local wound and skin pain before dressing removal (Baker-Wong)
 
Pain at removal (Baker-Wong)
 
Pre-procedural or intra-procedural pain medication administration at the time of dressing removal (Concomitant Medical)
 
Local wound and skin pain immediately after dressing removal (Baker-Wong)

Investigation Code **MxBFlex_02** Final Version Approval date **2018-06-19**
Central Amendment 1 Approval date **2018-11-08**

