Central Amendment 2 Approval date

	12-item Short Form Survey (SF12) Comfort and conformability Comfort during wear of the dressing (Very Poor/Poor/Good/Very Good/NA) Overall impression of the dressing (Very Poor/Poor/Good/Very Good/NA) Bulkiness of the dressing (Very Poor/Poor/Good/Very Good/NA) Friction of the dressing (Very Poor/Poor/Good/Very Good/NA) Appearance of dressing is discreet (Very Poor/Poor/Good/Very Good/NA) The stay-on-ability of the dressing (Very Poor/Poor/Good/Very Good/NA) Dressing stick to "hairy" skin (Very Poor/Poor/Good/Very Good/NA) Showerability of the dressing (Very Poor/Poor/Good/Very Good/NA)
	Investigator Reported outcomes Ease of handling (Very Poor/Poor/Good/Very Good/NA) Ability to maintain its integrity (Very Poor/Poor/Good/Very Good/NA) Ease of application (Very Poor/Poor/Good/Very Good/NA) Ability to be repositioned (Very Poor/Poor/Good/Very Good/NA) Conformability (Very Poor/Poor/Good/Very Good/NA) Ability to stay in place (Very Poor/Poor/Good/Very Good/NA)

Investigation Code **MxBFlex_02** **Final Version** **Approval date** **2018-06-19**
Central Amendment 1 Approval date **2018-11-08**
Central Amendment 2 Approval date

	Ease of removal (Very Poor/Poor/Good/Very Good/NA) Does the dressing cause skin stripping (Y/N) Presence of material remnant (None, Some) Is dressing adherent to the wound bed? (No/Yes, mild adhesion without bleeding/Yes, severe adhesion with bleeding) Wound re-injury or trauma to skin upon removal (Y/N) Exudate absorption even under compression (Y/N) Trauma to wound edges (Y/N)
Additional Endpoint	Outcome variable
Safety Evaluation	Number of safety events, not device related, associated with each of the wound dressings (AEs/SAEs)

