4.8.3 Determination of Sample Size

The expected mean differences in days to strikethrough between the differences Period 1-Period 2 between the two groups Mepilex® Border Flex and active control will be two times the difference in the effect Mepilex® Border Flex minus active control.

We estimate (assume) the SD for the difference in time to strikethrough between Period 2 and Period 1 to be 0.65 days both in the group started with Mepilex® Border Flex and in the group started with active control.

In order to find a difference in one half day between days to strikethrough between Mepilex® Border Flex and active control with a power of 80% a total of 16 evaluable subjects is needed.

This implies that in the first cross-over study 16 subjects will be randomized to the sequence Mepilex® Border Flex in the first period and Optifoam in the second period and to the sequence Optifoam in the first period and Mepilex® Border Flex in the second period in proportions 1:1.

In the second cross-over study 16 subjects will be randomized to the sequence Mepilex® Border Flex in the first period and Allevyn Life in the second period and to the sequence Allevyn Life in the first period and Mepilex® Border Flex in the second period in proportions 1:1. Both

Investigation Code	MxBFlex_02	Final Version	Approval date	2018-06-19
		Central Amendment 1	Approval date	2018-11-08
		Central Amendment 2	Approval date	

the randomizations above will be stratified by diagnosis Venous Leg Ulcer / Diabetic Foot Ulcer.

A total of 32 subjects will be included in the two cross-over studies.

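### On its natural reading, 4.8.1 tests ordered outcomes only as improved, not changed or worsened, which costs power, and more so the more wounds improve in Period 2

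*Combined protocol and SAP*

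**What the plan says.** Section 4.8.1 gives one scheme for all efficacy variables. It expects a period effect: "it is likely the status of the wounds will be better in the second period of the cross-over". It therefore works with within-subject changes: "For all subjects the difference in the efficacy variable between Period 2 and Period 1 in the cross-over will be calculated". Then: "These differences will then be compared between subjects started with Mepilex® Border Flex in Period 1 and subjects started with active control in Period 1", using what it calls an optimal two-sided test.

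The scheme then divides by type of variable. Continuous variables, including days to strikethrough, go into a Fisher permutation test on the full difference. For ordered categorical and dichotomous variables, "the differences, number and percentages improved, not changed and worsened, will be analyzed with Mantel-Haenszel Exact Chi-square test". The level is common to all: "All statistical tests will be two-sided and conducted at the 5% significance level".

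Section 4.6.2 lists many multi-level ordered outcomes. Wound status includes exudate amount (four levels), granulation (six levels), non-viable tissue and odor (five levels each), and maceration: "Skin maceration (None, Slight, Moderate, Severe". Ratings of the dressing itself have four levels plus NA, for example "Comfort during wear of the dressing (Very Poor/Poor/Good/Very Good/NA". There are 15 such ratings under subject-reported and investigator-reported outcomes, 8 and 7 respectively.

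**The concern.** A six-level scale gives a change between −5 and +5. Cut to three classes, a one-level and a three-level gain both count as improved. If wounds tend to be better in Period 2, many subjects in both sequences fall in that class whichever dressing they wore second. What separates the dressings is then mainly how far subjects moved, and that is no longer in the data being tested. Continuous outcomes keep this information.

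At stake is sensitivity on secondary outcomes in two small cross-overs. A real difference between dressings on, say, granulation or maceration could be missed and reported as no difference.

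**Working it through.** **The plan's own figure.** Section 4.8.3 says that "with a power of 80% a total of 16 evaluable subjects is needed" per cross-over, allocated 1:1. Its inputs are a dressing effect of 0.5 day, doubled to 1.0 day between sequences, and an SD of the period difference of 0.65 days. The normal approximation gives n per sequence = 2 × (1.960 + 0.842)² × 0.65² / 1.0² = 6.6, so 7. The noncentral t gives power 0.753 with 7 and 0.816 with 8 per sequence. So 16 is reproduced, and 8 per sequence is used below. The plan gives no power for any ordered outcome.

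**Assumed, because the documents are silent.** Latent normal score with SD 1 in each period, within-subject correlation 0.6, dressing effect 0.8 SD, period improvement of 0 to 1.5 SD, scales of 4 and 6 levels. The SD of the period difference is √(2 × (1 − 0.6)) = 0.894. The standardised contrast between sequences is 2 × 0.8 / 0.894 = 1.79, against 1.0 / 0.65 = 1.54 for the primary endpoint, so the assumed effect is of similar order.

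**Mechanism.** Ignoring ties, the probability of improving is Φ((shift + 0.8)/0.894) when the better dressing comes second and Φ((shift − 0.8)/0.894) when it comes first.

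| Period shift (SD) | Better dressing second | Better dressing first | Gap |
|---|---|---|---|
| 0 | 0.81 | 0.19 | 0.63 |
| 0.5 | 0.93 | 0.37 | 0.56 |
| 1.0 | 0.98 | 0.59 | 0.39 |
| 1.5 | 0.99 | 0.78 | 0.21 |

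The gap in mean latent difference stays at 2 × 0.8 = 1.6 SD in every row. The gap in the share improved shrinks.

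**Power.** Exact tests by full enumeration of the 12,870 ways to split 16 subjects 8 and 8. Each cell shows the three-class test against the exact Wilcoxon test on the full category differences, in percent (4,000 trials per setting; ceiling row 1,500). The ceiling row anchors the cut-points to control in Period 1, so improvement can run into the top category.

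| Scale | Shift 0 | 0.5 SD | 1.0 SD | 1.5 SD |
|---|---|---|---|---|
| 6 levels | 69 vs 81 | 60 vs 79 | 37 vs 74 | 13 vs 67 |
| 4 levels | 64 vs 73 | 57 vs 71 | 40 vs 65 | 18 vs 57 |
| 4 levels, ceiling | 65 vs 74 | 53 vs 65 | 32 vs 48 | 21 vs 35 |

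Independent repeats at 1.0 SD gave 36 vs 77 (6 levels), 40 vs 67 (4 levels) and 36 vs 51 (4 levels, ceiling). The loss is therefore 9 to 12 points with no shift. At 1.0 SD it runs from 51 − 36 = 15 to 77 − 36 = 41 points. In relative terms at 1.0 SD it is (74 − 37)/74 = 50% on six levels, (65 − 40)/65 = 38% on four levels, and (48 − 32)/48 = 33% on four levels with a ceiling.

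**A second data model**, with the shift counted in categories and the exact linear-by-linear test applied to the full difference or to its sign, agrees in direction. On six levels with an effect of 0.75 category and within-period SD 0.5, power is 0.86 vs 0.84 at no shift, 0.85 vs 0.76 at half a category, 0.83 vs 0.54 at one category and 0.78 vs 0.15 at 1.5 (full difference first). Over the whole assumed grid the relative loss is about 1–26%, 1–32%, 8–57% and 30–97% at those four shifts.

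**Type I error.** With no dressing effect and a 1.0 SD shift, the three-class test rejects in about 0.7% (6 levels) and 1.4% (4 levels) of trials. In the second model it rejects in 0.0 to 2.6% over shifts of 0 to 2 categories. All are below 5%.

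**Dichotomous outcomes.** The difference is already −1, 0 or +1, so the two tests coincide and nothing is lost.

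**The case against.** **The sentence may not mean this.** Its grammatical subject is the differences, and the three classes are inserted after it. Section 4.8.1 also uses numbers and percentages as its descriptive format for categorical variables. An exact Mantel-Haenszel test on the full ordered differences would be close to what is proposed here. This stands as an ambiguity. The three-class reading is the more natural one, and two programmers could implement different tests from the same sentence.

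**A reader might infer that collapsing undoes the period adjustment.** It does not. The classes are still compared between sequences, so a common period effect cancels when the dressings are equal. The type I error figures show this.

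**A reader might infer that half the power is lost under the improvement the plan expects.** The plan says only that better wound status is likely and gives no size. A loss of half needs about 1.0 SD on a six-level scale, or in most settings of the second model about 1.5 categories. At half a category or 0.5 SD the loss is mostly modest. Where the scale has a ceiling, part of the loss comes from the scale itself, and no change of test recovers it.

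**The period argument does not reach every ordered item.** The stated expectation concerns wounds. Nothing in the documents suggests that ratings such as bulkiness or ease of application will improve in weeks 3 and 4. For these the no-shift loss of about 10 points applies.

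**The outcomes are secondary.** The plan's only power claim concerns days to strikethrough, which is unaffected. This limits the consequence but does not remove the gain from specifying the more sensitive test.

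**Conclusion.** The point holds as a conditional loss of power on multi-level ordered secondary outcomes. It does not show a failed adjustment or an invalid test. On the natural reading of 4.8.1 the planned test is conservative, and it was less powerful than a test on the full differences at every shift examined on multi-level scales. The loss is about 10 percentage points with no period shift and about 15 to 40 points at a 1.0 SD shift. It reaches half the power or more only with large shifts.

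These sizes rest on 8 subjects per sequence from the plan and on an assumed effect of 0.8 SD, correlation of 0.6 and range of shifts, none of which the documents give. Wound-status scales such as granulation, exudate amount and maceration are the most exposed. Days to strikethrough, other continuous outcomes and dichotomous outcomes are untouched. This is a cheap improvement.

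**What to change.** In 4.8.1, state that for ordered categorical variables the full Period 2 minus Period 1 category difference is compared between the two sequences with an exact Wilcoxon rank-sum test. The Fisher permutation test already planned for continuous variables, or an exact linear-by-linear test, would also serve if applied to the full difference. Name one of them before database lock. Keep improved, not changed and worsened as a descriptive table, and keep the Mantel-Haenszel exact test for dichotomous variables.

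This costs wording only: no new data, visits or subjects. The one small price is accepting that a two-step change ranks above a one-step change, wherever on the scale it occurs.

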4.8.2 Primary Efficacy Analysis

Primary efficacy analysis comparison of days to strikethrough between Mepilex® Border Flex and active control will be performed on the full analysis set (FAS) in the following way.

For subjects randomized to Mepilex® Border Flex in the first period the difference in days to strikethrough between period 2 (active control) and period 1 (Mepilex® Border Flex) will be compared to subjects randomized to active control in the first period regarding the differences in days to strikethrough between period 2 (Mepilex® Border Flex) and period 1 (active control) with two-sided Fisher's non-parametric permutation tests at significance level 0.05. Period adjusted mean differences in days to strikethrough between Mepilex® Border Flex and active control will be given with 95% confidence interval based on Fisher's non-parametric permutation tests.

In both cross-over studies, Mepilex® Border Flex compared to Optifoam study and Mepilex® Border Flex compared to Allevyn Life, the same above analysis will be the primary analyses. Since there are two separated studies no multiplicity adjustment will be performed.

4.8.3 Determination of Sample Size

The expected mean differences in days to strikethrough between the differences Period 1-Period 2 between the two groups Mepilex® Border Flex and active control will be two times the difference in the effect Mepilex® Border Flex minus active control.

We estimate (assume) the SD for the difference in time to strikethrough between Period 2 and Period 1 to be 0.65 days both in the group started with Mepilex® Border Flex and in the group started with active control.

In order to find a difference in one half day between days to strikethrough between Mepilex® Border Flex and active control with a power of 80% a total of 16 evaluable subjects is needed.

This implies that in the first cross-over study 16 subjects will be randomized to the sequence Mepilex® Border Flex in the first period and Optifoam in the second period and to the sequence Optifoam in the first period and Mepilex® Border Flex in the second period in proportions 1:1.

In the second cross-over study 16 subjects will be randomized to the sequence Mepilex® Border Flex in the first period and Allevyn Life in the second period and to the sequence Allevyn Life in the first period and Mepilex® Border Flex in the second period in proportions 1:1. Both

Investigation Code	MxBFlex_02	Final Version	Approval date	2018-06-19
		Central Amendment 1	Approval date	2018-11-08
		Central Amendment 2	Approval date	

the randomizations above will be stratified by diagnosis Venous Leg Ulcer / Diabetic Foot Ulcer.

A total of 32 subjects will be included in the two cross-over studies.

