4. INVESTIGATION PLAN AND PROCEDURES

4.1 Overall Design and Flow Chart

Study Design

Prospective, randomized, controlled clinical trial (RCT) using a 2x2 cross-over (repeated measures) design to evaluate safety and efficacy. The study will be conducted in an outpatient setting of an academic clinical center.

Each subject will be randomly assigned to one of four treatment groups. The treatments and treatment schedule are detailed in the table below:

Table 1. Treatment Groups

	Treatment Group 1	Treatment Group 2	Treatment Group 3	Treatment Group 4
Week 1	Tr. B	Tr. A	Tr. C	Tr. A
Week 2	Tr. B	Tr. A	Tr. C	Tr. A
Week 3	Tr. A	Tr. B	Tr. A	Tr. C
Week 4	Tr. A	Tr. B	Tr. A	Tr. C

*A=Study Product, B=Comparator Product 1, C=Comparator Product 2

Approximately 40 subjects will be enrolled to have 32 subjects for the evaluation. Approximately 50% of the subjects will be in the VLU group and 50% of the subjects in the DFU group. Treatment sequence will be randomized so that a fair distribution is achieved. The total duration of the study will be approximately 4 weeks or 28 ± 2 days.

Visit Schedule

Potential study subjects will be screened for eligibility. Inclusion and exclusion criteria, vital signs, medical record reviews, subject demographics and informed consent will be performed and obtained at the Screening Visit (Day 0). If the patient meets the study eligibility criteria, he or she will be asked to sign consent. Study subjects will be randomized into one of four treatment groups. The test wound dressing will be applied at screening (Day-0) and evaluations will take place twice weekly throughout the Treatment Period. The scheduled dressing change will be on Day 7 of each treatment week (e.g. Visit Days 7, 14, 21 and 28), unless a dressing change is necessary because of strikethrough loss of adherence or discomfort. There will be a total of 8 visits to the Wound Care Center during the Treatment Period. During those visits, evaluations will be performed to assess the condition of the wound dressing, the wound, wound pain and patient comfort.

Investigation Code	MxBFlex_02	Final Version	Approval date	2018-06-19
		Central Amendment 1	Approval date	2018-11-08
		Central Amendment 2	Approval date	

All study evaluations will be performed by a study doctor or nurse during the follow-up visit at the Wound Care Center.

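### Both randomisations are stratified by VLU/DFU, but the primary permutation test and its 95% CI ignore diagnosis: an efficiency loss if the two diagnoses change differently between periods

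*Combined protocol and SAP*

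**What the plan says.** Section 4.8.3 randomises 16 subjects 1:1 to the two sequences in each AB/BA cross-over and states that "the randomizations above will be stratified by diagnosis Venous Leg Ulcer / Diabetic Foot Ulcer". Section 4.1 aims for roughly half VLU and half DFU, so a balanced cross-over has 4 subjects per diagnosis per sequence.

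The analysis does not use that factor. Section 4.8.1 forms each subject's Period 2 minus Period 1 difference and continues: "These differences will then be compared between subjects started with Mepilex® Border Flex in Period 1", against those who started with the control. Section 4.8.2 tests this contrast "with two-sided Fisher's non-parametric permutation tests at significance level 0.05" and reports a "95% confidence interval based on Fisher's non-parametric permutation tests". Categorical outcomes "will be analyzed with Mantel-Haenszel Exact Chi-square test", again with no stratum named. Period is the only adjustment, introduced because "it is likely the status of the wounds will be better in the second period of the cross-over". No sensitivity analysis by diagnosis is given. The only item split by wound type is the health-economic count of dressing changes per week (section 2).

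The sample size assumes an SD of 0.65 day for the period difference, "both in the group started with Mepilex® Border Flex and in the group started with active control". The natural reading is the SD across both diagnoses within a sequence, but the text does not say so.

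**The concern.** A permutation test takes its reference distribution from the way subjects were allocated. Here they are allocated within diagnosis, but the planned test also counts allocations that stratification is meant to prevent. If VLU and DFU subjects change differently from Period 1 to Period 2, that gap stays in the pooled error term. The test then becomes conservative and its interval wider than necessary.

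A second effect comes from dropout. According to section 4.1, "Approximately 40 subjects will be enrolled to have 32 subjects for the evaluation", and section 4.3.4 does not replace subjects who discontinue. The evaluable strata may therefore be uneven between sequences. A gap would then move the pooled estimate, in a direction set by chance.

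Each cross-over has only 16 evaluable subjects and is powered barely above 80%, so a few points of power matter.

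**Working it through.** **Inputs from the plan (4.8.3, 4.8.2, 4.1).** Treatment effect τ = 0.5 day; sequence contrast 2τ = 1.0 day; SD of the period difference 0.65 day; two-sided 0.05; 8 subjects per sequence; about 50/50 VLU/DFU.

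**Assumed, because the documents give no figure.** The VLU minus DFU gap g in mean Period 2 minus Period 1 change, averaged over sequences: 0, 0.25, 0.5, 0.75 or 1.0 day.

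**1. Reproduce the plan's figure.** With 8 per sequence the noncentrality is 1.0 / (0.65 × √(2/8)) = 3.08 on 14 df, which gives 81.6% power. With 7 per sequence power is 75.3%. The plan's 16 is therefore right.

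**2. What differencing removes.** A constant VLU/DFU difference in wear time appears in both periods and cancels. Only g remains. With equal strata, total variance = within-diagnosis variance + g²/4. Holding the total SD at 0.65, the within-diagnosis SD at g = 0.5 is √(0.4225 − 0.0625) = 0.60. At g = 0, 0.25, 0.75 and 1.0 it is 0.65, 0.64, 0.53 and 0.42.

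**3. The two reference sets.** Pooled: C(16,8) = 12,870 allocations. Within diagnosis: C(8,4)² = 70² = 4,900.

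**4. Balanced strata, total SD 0.65.** All allocations were enumerated in 20,000 simulated normal trials per row (Monte Carlo error about 0.3 point); CI widths come from inverting each test in 300 trials per row. Stratified type I error is 4.7%.

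| Gap (day) | Power, pooled / stratified (%) | Type I error, pooled (%) | Mean CI width, pooled / stratified (day) |
|---|---|---|---|
| 0 | 81.7 / 81.0 | 4.7 | 0.69 / 0.70 |
| 0.25 | 81.9 / 82.4 | 4.3 | 0.69 / 0.69 |
| 0.5 | 82.9 / 87.0 | 3.2 | 0.70 / 0.65 |
| 0.75 | 84.5 / 93.4 | 1.6 | 0.70 / 0.57 |
| 1.0 | 88.3 / 99.4 | 0.2 | 0.72 / 0.45 |

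With non-normal differences at a 0.5-day gap, power is 87.8/89.9% (t with 3 df) and 84.2/86.7% (centred exponential), from 6,000 trials each.

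**5. If 0.65 is a within-diagnosis SD.** Pooled/stratified power is 80.4/81.0% at 0.25 day and 76.7/81.0% at 0.5 day.

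**6. Uneven evaluable strata, gap 0.5 day, total SD 0.65.** The shift in the pooled estimate is g × (VLU share in one sequence − VLU share in the other) / 2.
- VLU 6/5, DFU 2/3: 0.5 × (6/8 − 5/8)/2 = 0.031 day. Pooled power is 77% or 87% by direction of the gap; stratified 86%.
- VLU 5/3, DFU 3/5: 0.5 × (5/8 − 3/8)/2 = 0.0625 day. Pooled power is 71% or 91% by direction; stratified 84%.

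The stratified estimate does not shift in either layout.

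**7. Where stratifying loses.** With no gap, pooled/stratified power is 81.6/80.5% for 6/5 and 2/3, and 81.4/78.2% for 5/3 and 3/5. If only the treatment effect differs by diagnosis, by 0.25, 0.5, 0.75 or 1.0 day, it is 82.0/81.3, 82.8/81.8, 84.4/83.0 and 88.2/87.0% (total SD 0.65). With 0.65 as the within-diagnosis SD it is 62.6/60.3% at 1.0 day. If period change and effect both differ by 0.5 day, stratifying is ahead: 84.1/88.1%.

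**The case against.** The strongest case against is that the benefit rests on a gap the documents never state. Section 4.8.1 expects improvement in Period 2 but draws no distinction by diagnosis. A gain of about 4 points needs a gap of 0.5 day, as large as the treatment effect the trial is sized to detect. With balanced strata and a total SD of 0.65, pooled power stays above 80% at every gap, so stratifying adds margin but rescues nothing. All of this stands.

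The uneven layouts are also uncommon. Suppose 20 are enrolled per cross-over, 5 in each diagnosis-by-sequence cell, and four are lost at random. The 5/3 and 3/5 pattern, in either direction, then has probability 2 × C(5,2)² / C(20,4) = 200/4,845 = 4.1%, and the mean absolute shift at a 0.5-day gap is about 0.02 day. The 6/5 and 2/3 layout cannot arise from 5 per cell; it needs a diagnosis mix further from 50/50. These layouts show what can happen, not what is expected.

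Finally, the change needs a protocol amendment (section 4.9) late in the trial. The cover page is dated mid-May 2019, section 6 plans to complete inclusion that month, and section 4.7.3 lets authorised sponsor staff view data on entry. That is a reason to date and justify the change before database lock. It does not make the pooled reference set match the randomisation.

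**Conclusion.** The point holds, as one of efficiency. The primary test and interval omit the factor both randomisations are stratified on, and the plan gives no reason. The sample size is correct, and type I error was not inflated in any scenario run.

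On the natural reading of the SD with balanced strata, stratifying gains about 4 points of power at a 0.5-day gap and under 1 point at 0.25 day; with no gap it loses under 1 point. Balanced pooled power falls below 80% only if 0.65 day is a within-diagnosis SD, and then by a 0.5-day gap, not at 0.25 day. With uneven strata and a gap, pooled power can fall below or rise above the stratified figure. Where it rises, it does so through a shifted estimate.

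Confidence is medium, because everything beyond the textual mismatch depends on the assumed gap and, for the power figures, mostly on normal differences.

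**What to change.** - **Section 4.8.2.** Permute sequence labels within VLU and within DFU, holding the observed number per sequence in each. Estimate the effect as half the weighted mean of the within-diagnosis sequence contrasts, with prespecified weights n1·n2/(n1+n2), where n1 and n2 are the stratum's evaluable sequence counts. A stratum with an empty sequence gets weight 0; say openly that its subjects then do not contribute. Invert the same test for the 95% CI. Keep the pooled test as a sensitivity analysis.
- **Section 4.8.1.** State whether the other variables follow (permutation within diagnosis; Mantel-Haenszel exact test with diagnosis as stratum) or whether the change applies to the primary only.
- **Section 4.8.3.** Add a clause saying whether 0.65 day is the SD across both diagnoses.

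If the sponsor will not change the primary test this late, a prespecified stratified sensitivity analysis is the lesser option. It shows whether diagnosis matters but recovers no power for the primary.

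The cost is wording, made through the section 4.9 amendment process before database lock. N, visits and procedures are unchanged. With no gap, the power lost is under 1 point in balanced strata and about 3 points in the 5/3 and 3/5 layout. If only the treatment effect differs by diagnosis, it is about 1 to 2 points. The reference set falls to 4,900 allocations, or C(8,5) × C(8,3) = 3,136 in that uneven layout, which is still ample for a 5% test.
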